## 4.4. Tertiary Analyses

## 4.4.1. Definition of endpoint

CCI

## 4.4.2. Main analytical approach

Not applicable

## 4.5. Interim Analyses

There are no interim analyses planned for this study.

## 4.5.1. Sequence of analyses

A final analysis will be conducted once all the immunogenicity data are available for the primary endpoint. This final analysis will include immunogenicity and safety data up to Visit 2 (Day 31). The individual data listings and participant treatment assignments will not be provided at this time.

An end-of-study analysis with all data including the data obtained until 6 months post-vaccination will be performed.

Note that the GSK central study team (Clinical Research and Development Lead, Statistician, Safety Representative, etc.) will be unblinded to the details of the study intervention lots at the time of final analysis in order to prepare the CSR of the final analysis.

## 4.5.2. Statistical considerations for interim analysis

Not applicable.

## 4.6. Changes to Protocol Defined Analyses

Not applicable.

### 5. SAMPLE SIZE DETERMINATION

The target enrolment will be 750 participants based on the assumptions described below:

### Primary Objectives:

- **Endpoint:** RSVPreF3 IgG specific antibody concentration at 1-month post-vaccination (Day 31).
- **Group level summary:** Antibody geometric mean concentration (GMC) per group.
- Reference for the sample size calculation: A standard deviation (SD) of the log10-transformed concentrations of 0.45 is used as reference. It is the highest SD observed in the RSV OA=ADJ 002 (208851) study among all treatment groups and humoral assays.
- Success criteria for consistency: the 2 sided 95% confidence interval (CI) of the GMC ratios between each pair of the 3 lots is within the pre-defined clinical limit of [0.67, 1.5].
- **Null hypothesis:** At least 2 of the 3 vaccine lots differ by more than 1.5-fold (1 sided non-inferiority limit) with respect to their GMC.

- **Alternative hypothesis:** Clinical equivalence (consistency) between each pair of the 3 lots with respect to their GMCs.
- **Type I error:** a 1-sided alpha of 2.5% will be used for the 6 non inferiority tests, no adjustment of Type 1 error is needed because all the lot-to-lot consistency criteria have to be met simultaneously
- **Type II error:** Considering a Bonferroni correction for multiplicity, the global Type II error will be equal to 6 time the nominal Type II error calculated for one non inferiority test. The sample size is determined to reach a global power of at least 90%.

Table 2 shows that the probability (global power) to reach the lot-to-lot consistency criterion with 225 evaluable participants in each vaccine lot group is at least 91%, with a 1-sided alpha = 0.025.

Table 2 Power to demonstrate consistency between each pair of the 3 lots in terms of RSVPreF3 IgG GMCs with 225 evaluable participants per group

Vaccine component	Endpoints	Reference SD*	Clinically acceptable bounds for consistency	N per group	1-sided alpha	Power	Type II error
RSVPreF3 IgG-specific	GMC	0.45	[0.67, 1.5]	225	0.025	91%	9%

GMC: geometric mean concentration; Ig: immunoglobin; N = number of participants; SD: Standard Deviation (of the log10 transformed concentration)

Pass 2019 (Non-Inferiority test of 2 independent means). Power = 100-the Type II error (Beta). The Type II error (Beta) has been adjusted using Bonferroni's method (overall Type II error = sum of the individual Type II errors) since 6 non-inferiority tests are needed for lot-to-lot consistency (nominal Beta for each non-inferiority test is 1.5%).

\* SD = 0.45 was selected based on the results from the RSV OA=ADJ-002 study. A conservative approach was used by selecting the highest value observed for SD across groups and humoral assays.

The primary objective analysis will be performed on the PPS. Assuming a 10% non-evaluable rate up to Day 31 (participants dropped-out or excluded from the PPS), a total of 750 participants (250 per group) will have to be enrolled in order to reach 225 participants evaluable for the primary objective.

Secondary Objectives: NA

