9. STATISTICAL CONSIDERATIONS

9.1. Statistical hypotheses

The assumptions, statistical hypotheses and success criteria associated to the primary objective to demonstrate the lot-to-lot consistency of 3 lots of the RSVPreF3 OA investigational vaccine in terms of immunogenicity at 30 days post-vaccination are described hereafter.

- **Endpoint:** RSVPreF3 IgG-specific antibody concentration at 1-month post-vaccination (Day 31).
- **Group level summary:** Antibody GMC per group.
- Reference for the sample size calculation: A standard deviation (SD) of the log₁₀ transformed concentrations of 0.45 is used as reference. It is the highest SD observed in the RSV OA=ADJ 002 (208851) study among all treatment groups and humoral assays.
- Success criteria for consistency: the 2 sided 95% confidence interval (CI) of the GMC ratios between each pair of the 3 lots is within the pre-defined clinical limit of [0.67, 1.5].
- **Null hypothesis:** At least 2 of the 3 vaccine lots differ by more than 1.5-fold (1 sided non-inferiority limit) with respect to their GMC.
- **Alternative hypothesis:** Clinical equivalence (consistency) between each pair of the 3 lots with respect to their GMCs.
- **Type I error:** a 1-sided alpha of 2.5% will be used for the 6 non-inferiority tests.
- **Type II error:** Considering a Bonferroni correction for multiplicity, the global Type II error will be equal to 6 time the nominal Type II error calculated for 1 non-inferiority test. The sample size is determined to reach a global power of at least 90%.

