9.5. Sample size determination

Table 15 shows that the probability (global power) to reach the lot-to-lot consistency criterion (Section 9.1) with 225 evaluable participants in each vaccine lot group is at least 91%, with a 1-sided alpha = 0.025.

Table 15 Power to demonstrate consistency between each pair of the 3 lots in terms of RSVPreF3 IgG GMCs with 225 evaluable participants per group

Vaccine component	Endpoints	Reference SD*	Clinically acceptable bounds for consistency	N per group	1-sided alpha	Power	Type II error
RSVPreF3 IgG-specific	GMC	0.45	[0.67, 1.5]	225	0.025	91%	9%

GMC: geometric mean concentration; Ig: immunoglobin; N = number of participants; SD: Standard Deviation (of the log₁₀ transformed concentration)

Pass 2019 (Non-Inferiority test of 2 independent means). Power = 100-the Type II error (Beta). The Type II error (Beta) has been adjusted using Bonferroni's method (overall Type II error = sum of the individual Type II errors) since 6 non-inferiority tests are needed for lot-to-lot consistency (nominal Beta for each non-inferiority test is 1.5%).

* SD = 0.45 was selected based on the results from the RSV OA=ADJ-002 study. A conservative approach was used

SD = 0.45 was selected based on the results from the RSV OA=ADJ-002 study. A conservative approach was used by selecting the highest value observed for SD across groups and humoral assays.

The primary objective analysis will be performed on the PPSi. Assuming a 10% non-evaluable rate up to Day 31 (participants dropped-out or excluded from the PPSi), a total of approximately 750 participants (250 per group) will have to be enrolled in order to reach 225 participants evaluable for the primary objective.

Participants who withdraw from the study will not be replaced.

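### Does the stated 91% power fail because it assumes that all three lots have identical true GMCs?

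*SAP*

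**What the plan says.** Protocol 9.1 sets the aim: "The sample size is determined to reach a global power of at least 90" percent. SAP section 5 reports that "the probability (global power) to reach the lot-to-lot consistency criterion with 225 evaluable participants in each vaccine lot group is at least 91" percent. Success requires the two-sided 95% confidence interval of the GMC ratio for every pair of lots to lie "within the pre-defined clinical limit of [0.67, 1.5"].

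The inputs are set out in Protocol 9.1 and 9.5 and in SAP section 5:

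- Spread: "A standard deviation (SD) of the log10-transformed concentrations of 0.45 is used as reference". The reason given is "A conservative approach was used by selecting the highest value observed for SD across groups and humoral assays".
- Error rate: "a 1-sided alpha of 2.5% will be used for the 6 non inferiority tests".
- Type II error: summed over six tests by Bonferroni, where the "nominal Beta for each non-inferiority test is 1.5" percent.
- Numbers: 225 evaluable per group from 250 enrolled, allowing for 10% non-evaluable.

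The assumed true ratio between lots is not in either list, and no power is given for any other ratio.

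**The concern.** The alternative hypothesis covers every ratio up to 1.5-fold, so power has no single value until one point in that range is named. The documents do not name one. Working back from the nominal type II error shows that the point used is exact equality of all three lots, which is the favourable end of the range. Read literally, a power of at least 91% sounds like a floor. In fact it is a floor only relative to the Bonferroni approximation, with identical lots.

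A second doubt concerns the limits. The calculation appears to use 1.5 on both sides, whereas the stated lower limit of 0.67 is slightly tighter than 1/1.5.

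If real lots differ by a few percent, power at SD 0.45 drops below the 90% target. A missed limit could then be read as inconsistency between lots when it reflects limited power.

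**Working it through.** **Inputs** (Protocol 9.1 and 9.5; SAP section 5): n = 225 per group, SD = 0.45 on the log10 scale, one-sided alpha 0.025, limits [0.67, 1.5], six one-sided tests. The true ratio is not stated; take it as 1.

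**Step 1: reproduce the plan's figure.**

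- Standard error of a pairwise difference: 0.45 × √(2/225) = 0.0424.
- Margin: log10(1.5) = 0.1761.
- Noncentrality: 0.1761 / 0.0424 = 4.15, on 2 × 225 − 2 = 448 degrees of freedom.
- Type II error per test from the noncentral t: 1.457%, which is the plan's 1.5%.
- Bonferroni sum: 6 × 1.457% = 8.74%, so global power is 91.3%, the plan's 91%.
- Enrolment: 225 / 0.9 = 250 per group.

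The figure is reproduced, and it requires a true ratio of 1.

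**Step 2: use the stated lower limit.** Here −log10(0.67) = 0.1739, and the type II error per test is 1.656%.

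- Three tests at each limit: 3 × 1.457% + 3 × 1.656% = 9.34%, so 90.7%.
- All six tests at 0.67: 6 × 1.656% = 9.94%, so 90.1%.

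Both exceed the 90% target. Both are also only Bonferroni bounds. The probability that all three intervals lie inside [0.67, 1.5] with equal lots, found by simulation with a pooled SD on 3 × 225 − 3 = 672 degrees of freedom, is 92.2%. The claim of at least 91% is therefore true for the event it describes when lots are identical.

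**Step 3: let the lots differ.** Joint power from the same simulation, with 225 per group, is tabulated below. Ranges reflect the direction of the difference, because the limits are slightly asymmetric. The SD of 0.40 is an assumption; the documents give no second value.

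| Largest true ratio | SD 0.45, one lot off | SD 0.45, evenly spread | SD 0.40, one lot off | SD 0.40, evenly spread |
|---|---|---|---|---|
| 1.00 | 92% | 92% | 98% | 98% |
| 1.05 | 88–89% | 89–90% | 96% | 96–97% |
| 1.10 | 78–80% | 82–83% | 89–90% | 92% |

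At SD 0.45 the plan's own Bonferroni figure, with a 1.5-fold margin on both sides, crosses 90% at a ratio of about 1.03. Joint power crosses at about 1.04 to 1.05.

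**Step 4: how far the SD must fall to offset this.** If 0.45 is the unadjusted SD and the baseline titer has correlation ρ with the Day 31 titer, the residual SD is 0.45 × √(1 − ρ²). A residual SD of 0.40 needs ρ = √(1 − (0.40/0.45)²) = 0.46. To bring joint power back to about 90% when one lot is off by 1.05, a residual SD of about 0.445 is enough, or ρ = √(1 − (0.445/0.45)²) ≈ 0.15. The documents give no correlation, so these values show sensitivity only.

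**The case for a change.** The strongest case for a change is that a power statement should name the alternative at which it holds. SAP section 5 says it describes its assumptions, and this one is absent. A conservative SD does not make the statement unconditional: at SD 0.40 it moves the point where power falls below 90% from about a 5% lot difference to about 10%, and larger differences still lose power. One stated cautious input beside one unstated favourable input is a reason to show both.

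This stands as a point about reporting. The true ratio of 1 is not written down, and a phrase giving it would make the sentence more exact.

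The rest does not stand. Calling 91% a best case holds only with the SD fixed at 0.45. That SD is the highest seen across groups and humoral assays in the earlier study. The primary ANCOVA adjusts for pre-dose titer and age category with no variance reduction credited, and the Bonferroni sum is about one point below joint power for equal lots. The documents contain no data on lot-to-lot variation, so a 1.05- or 1.10-fold difference is the reader's choice of scenario and not a value the plan ignored. The point about 0.67 shows no false figure: 90.7% rounds to the tabulated 91%, and the exact joint probability is higher.

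**Conclusion.** No change to the plan is needed. The 91% is correct on the documents' inputs and meets the 90% target. It is conditional on SD 0.45 and on a true ratio of 1 between all lots. Equality of lots is a conventional planning assumption for a consistency trial, and any statistician can recover it from the stated SD, sample size, alpha, margin and nominal type II error.

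The size of the effect is real but bounded. At SD 0.45, power falls from about 92% to 88–90% at a 1.05-fold difference and to 78–83% at 1.10-fold. At an assumed residual SD of 0.40, a 1.10-fold difference still gives about 89–92%.

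Nothing in the analysis depends on this figure. The decision rests on the three confidence intervals, the type I error is unaffected, and lower power raises only the risk that the trial fails, not the risk of a false claim of consistency. If a limit is crossed, the width and position of the interval will show whether precision or a lot difference is responsible, and a planning table would add nothing to that reading. The omission is missing detail that a reader can fill in.

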## 6. SUPPORTING DOCUMENTATION

## 6.1. Appendix 1 Study Population Analyses

## 6.1.1. Participant Disposition

The number of participants who withdraw from the study will be tabulated by group according to the reason for drop-out. This analysis will be based on the ES and the PPS.

## 6.1.2. Demographic and Baseline Characteristics

The median, mean, range and standard deviation of age (in years) at vaccination will be computed by group. The center distribution, distribution of participants in each age category (60-69, 70-79,  $\geq$  65,  $\geq$  70 and  $\geq$ 80 years), geographical ancestry and sex composition will be presented. This analysis will be based on the ES and the PPS.

Medical history will be summarized respectively.

### 6.1.3. Protocol Deviations

The number of participants enrolled into the study as well as the number of participants excluded from per protocol set (PPS) analyses will be tabulated for the total population. This analysis, also broken down by study group, will be based on the ES.

The number of participants enrolled into the study as well as the number of participants excluded from per the ES will be tabulated for the total population. This will be based on all enrolled participants.

## 6.1.4. Subject exposure

The number and percentage of participants who received the vaccine will be tabulated by group for the ES.

### 6.1.5. Prior and Concomitant Medications

The number and percentage of participants using concomitant medication (any medication, any antipyretic and any antipyretic taken prophylactically, respectively) during the 4-day follow-up period (i.e., on the day of vaccination and 3 subsequent days) and during the 30-day follow-up period (i.e., on the day of vaccination and 29 subsequent days) will be summarized by group after vaccine dose.

## 6.1.6. Additional Analyses Due to the COVID-19 Pandemic

A standardized MedDRA Query (SMQ) will be used to identify all COVID-19 AEs.

The overall incidence of COVID-19 AEs and SAEs, COVID-19 AEs leading to study intervention discontinuation, COVID-19 AEs leading to study withdrawal, and severe COVID-19 AEs will be summarized. The incidence of these events at individual PT level can be obtained from the standard AE/SAE summaries.

COVID-19 assessments (confirmed, probable and suspected diagnosis) for participants with COVID-19 AEs will be summarized.

The number and percentage of participants with concomitant vaccination (COVID-19) before and during the study will be tabulated with exact 95% CI.

## 6.2. Appendix 2 Data Derivations Rule

This section contains standard rules for data display and derivation for clinical and epidemiological studies.

## 6.2.1. Attributing events to vaccine doses

If an event starts on the same day as a study dose, the relative dose will be derived from the additional information provided in the case report form (CRF) using the contents of the flag indicating if the event occurred before or after study dose. The relative dose for the event will be the one administered on the start day of the event.

### 6.2.2. Handling of missing data

#### 6.2.2.1. Dates

When partially completed dates (i.e. dates missing a day and/or month) are used in calculations, the following standard rules will be applied:

- A missing day will be replaced by 15
- A missing day and month will be replaced by June 30th.

The following exceptions apply:

When partially completed dates (i.e. with missing day or month) are used in calculations, the following rules will be applied:

- Adverse event start dates with missing day:
  - If the month is not the same as the vaccine dose, then the imputed start date will be the 1st of the month
  - If the event starts in the same month as the vaccine dose, the flag indicating if the event occurred before or after vaccination (AE.AESTRTPT) will be used to

complete the date. If 'after vaccination' is selected, the imputed start date will match the vaccine dose given during that month. If 'before vaccination' is selected, the imputed date will be one day before the vaccine dose given during that month.

- Adverse event start dates with missing day and month:
  - If the year is not the same as the vaccine dose, then the imputed start date will be the 1st of January.
  - If the event starts in the same year as the vaccine dose, the flag indicating if the event occurred before or after vaccination (AE.AESTRTPT) will be used to complete the date. If 'after vaccination' is selected, the imputed start date will match the first vaccine dose given during that year. If 'before vaccination' is selected, the imputed date will be one day before the first vaccine dose given during that year.
- Adverse event end dates with missing day: the imputed end date will be the last day of the month (30 or 31) or the study conclusion date whichever comes first.
- Adverse event end dates with missing day and month: the imputed end date will be the last day of the year (31st of December) or the study conclusion date whichever comes first.

All incomplete concomitant medication/vaccination start/end date will follow the rules above.

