5.2.2. Prior/Concomitant therapy

- Use of any investigational or non-registered product (drug, vaccine or medical device) other than the study intervention(s) during the period beginning 30 days before study intervention administration and ending 30 days after study intervention administration, or planned use during the study period.
- Planned or actual administration of a vaccine not foreseen by the study protocol in the period starting 30 days before and ending 30 days after the study intervention administration, with the exception of inactivated and subunit influenza vaccines which can be administered up to 14 days before or from 14 days after the study vaccination.

Note: In case an emergency mass vaccination for an unforeseen public health threat (e.g. a pandemic) is recommended and/or organized by the public health authorities, outside the routine immunization program, the time period described above can be reduced if necessary for that vaccine provided it is used according to the local governmental recommendations and that the Sponsor is notified accordingly.

- Previous vaccination with an RSV vaccine.
- Administration of long-acting immune-modifying drugs or planned administration at any time during the study period (e.g. infliximab).
- Administration of immunoglobulins and/or any blood products or plasma derivatives during the period starting 90 days before the administration of the study intervention or planned administration during the study period.
- Chronic administration (defined as more than 14 consecutive days in total) of immunosuppressants or other immune-modifying drugs during the period starting 90 days prior to the study intervention administration or planned administration during the study period. For corticosteroids, this will mean prednisone ≥ 20 mg/day or equivalent. Inhaled and topical steroids are allowed.

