8.2.1.3. Vaccination history

Obtain the participant's vaccination history by interviewing the participant and/or review of the participant's vaccination records.

217131 (RSV OA=ADJ-009) Protocol Final

Any vaccine administered up to 1 year before study intervention administration should be recorded in the eCRF with date of vaccination. For history of influenza vaccination, information about the vaccine formulation (e.g., adjuvanted or non-adjuvanted or high-dose, etc.) should be recorded.

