## 3.1.2. Elimination from Per Protocol set (PPS)

A participant will be excluded from the populations for analysis under the following conditions:

- For codes 800, 900, 1030, 1050 and 2020: participants will be eliminated for all
  visits
- For codes 1040, 1070, 1080, 1090, 2010, 2040 and 2050: participants will be eliminated from a specific visit (at which the condition is met) onwards.
- For codes 2090, 2100, 2120: participants will be eliminated at the specific visit at which the condition is met.

\*\* 30-42 days between Visit 1 and Visit 2.

Table 1 List of elimination codes

Code	Condition under which the code is used	Visit /Contact (timepoints) where the code is checked	Visit from when it is applicable	Applicable for analysis set/endpoint
800	Fraudulent data	All	All	ES and PPS for analysis of immunogenicity
900	Invalid informed consent	All	All	ES and PPS for analysis of immunogenicity
1030	Study intervention not administered at all	All	All	ES and PPS for analysis of immunogenicity
1040	Administration of concomitant vaccine(s) forbidden in the protocol Use of any investigational or non-registered product (drug, vaccine or medical device) other than the study intervention(s) during the period beginning 30 days before study intervention administration and ending 30 days after study intervention administration, or planned use during the study period.  Planned or actual administration of a vaccine not foreseen by the study protocol in the period starting 30 days before the study intervention administration and ending 30 days after the study intervention administration.  Note: In case an emergency mass vaccination for an unforeseen public health threat (e.g.: a pandemic) is recommended and/or organized by the public health authorities, outside the routine immunization program, the time period described above can be reduced if necessary for that vaccine provided it is used according to the local governmental recommendations and that the Sponsor is notified accordingly.	Visit 1,2 and contact 6 months post-vaccination	From the specific visit the condition is met	PPS for analysis of immunogenicity
1050	Randomization failure: Subject not randomized in the correct group (To be attributed by Statistician only; Check SBIR, replacement, vaccine administration)	Visit 1	All	PPS for analysis of immunogenicity

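### The SAP's partial-date rule sets a prior-month vaccination with a missing day to the 1st; if that date is used for the 30-day pre-dose window, nearly all true violations go undetected.

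*SAP*

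**What the plan says.** SAP 6.2.2.1 (Dates) governs partial dates used in calculations. Its general rule is "A missing day will be replaced by 15". Exceptions for adverse events follow:

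- Start date, day missing, different month: "If the month is not the same as the vaccine dose, then the imputed start date will be the" first day of that month.
- Start date, day missing, same month as the dose: the before/after flag decides. "If 'before vaccination' is selected, the imputed date will be one day before the vaccine dose given during that month".
- Start date, day and month missing, same year, flagged as before: one day before the dose.
- End date: "Adverse event end dates with missing day: the imputed end date will be the last day of the month", or the study conclusion date if earlier.

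The section closes with "All incomplete concomitant medication/vaccination start/end date will follow the rules above".

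SAP 3.1.2, Table 1, code 1040 removes a participant from the per-protocol set (PPS) for "Planned or actual administration of a vaccine not foreseen by the study protocol in the period starting 30 days before the study intervention administration", and for the 30 days after it. Code 2010 covers all inclusion and exclusion criteria, so it also reaches the vaccine criterion in protocol 5.2.2. That criterion has an exception for inactivated and subunit influenza vaccines, "which can be administered up to 14 days before or from 14 days after the study vaccination".

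Protocol 8.2.1.3 asks for vaccines of the past year with their dates, but allows recall as the source: "Obtain the participant's vaccination history by interviewing the participant and/or review of the participant's vaccination records".

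**The concern.** An onset rule and a washout rule serve different purposes. For a vaccine given in the month before dosing, the 1st is the most lenient day available: it gives the longest possible gap to the study dose.

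The rule is also inconsistent in how it treats precision. Take a study dose on 10 November 2021. A vaccine known only as given in 2021 before the dose is set to 9 November, which is a violation. One recorded as October 2021 is set to 1 October and passes. The less complete record is flagged and the more complete one is not.

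The PPS carries the primary lot-consistency analysis and is part of the primary estimand. The Exposed Set analysis is triggered only when more than 5% of vaccinated participants with serology in a group are excluded from the PPS, and a violator who passes through imputation does not count towards that trigger.

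**Working it through.** The plan gives no figure to reproduce here, so this is a calendar enumeration.

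**Inputs from the documents:** imputation to the 1st (SAP 6.2.2.1) and a 30-day pre-dose window (SAP Table 1, code 1040; protocol 5.2.2).

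**Assumptions not in the documents:** the true day is uniform within the prior month, and study doses are spread evenly over the 365 days of 2021. Since it is not stated whether day 30 itself is inside the window, both readings are run.

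**Step 1: does the imputed date pass?** Let L be the length of the prior month and d the dosing day of the month. The imputed gap is L − 1 + d days.

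- Day 30 inside: it passes if L − 1 + d > 30. It fails only on 1–3 March and on 1 May, 1 July, 1 October and 1 December, which is 7 dates. It passes on 358/365 = 98.1%.
- Day 30 outside: it fails only on 1 and 2 March. It passes on 363/365 = 99.5%.

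**Step 2: how many true dates are inside?** A vaccine on day x of the prior month lies L − x + d days before dosing. The number of days inside is min(L, 31 − d) with day 30 inside, and min(L, 30 − d), not below 0, with day 30 outside. Dividing by L gives the share.

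Example, dose on 10 November: L = 31 and d = 10, so the imputed gap is 31 − 1 + 10 = 40 days, a pass. True October dates inside: 21 of 31 (day 30 inside) or 20 of 31 (day 30 outside).

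Average share with day 30 inside, by length of the prior month: 49.95% (31 days, 210 dosing dates), 50.0% (30 days, 124 dates) and 53.2% (28 days, 31 dates). Weighted: (210 × 0.4995 + 124 × 0.500 + 31 × 0.532)/365 = 50.2%.

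**Step 3: violations missed**

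| Day 30 counted as | Imputed date passes | Truly inside | Inside and passes | Share of violations missed |
|---|---|---|---|---|
| inside | 98.1% | 50.2% | 48.3% | 48.3/50.2 = 96.2% |
| outside | 99.5% | 47.0% | 46.5% | 46.5/47.0 = 98.8% |

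**Step 4: sensitivity.** Season matters little, but dosing day matters a great deal. With day 30 inside, the true share inside by dosing day is:

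| Dosing day | 1 | 10 | 15 | 20 | 25 | 30 |
|---|---|---|---|---|---|---|
| Truly inside | 97–100% | 68–75% | 52–57% | 35–39% | 19–21% | 3–4% |

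**Step 5: other rules in the same section, day 30 inside.** Day 15 would flag 47.9% against 50.2% truly inside and misclassify 25.0%, with no marked direction. The last day of the month would flag 98.1%. The choice of rule therefore decides the result.

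**Step 6: scale.** The number of incomplete dates is not given. As an illustration only, if 1% to 3% of 750 participants had one non-study vaccine in the prior month with the day missing, that is 7.5 to 22.5 people. At 46.5% to 48.3%, about 3 to 11 would be kept wrongly, or roughly 1 to 4 per lot.

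**The case against.** The strongest objection is that nothing ties the imputed dates to the elimination codes. SAP 6.2 presents its rules as being for display and derivation, SAP 3.1.2 never refers to them, and protocol 9.2.1 says only that participants may be eliminated. This stands: the consequence is conditional. But 6.2.2.1 covers partial dates used in calculations, and no other rule is offered for a window that has to be calculated.

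Second, prior vaccines are collected as vaccination history, so the closing sentence might not reach them and the day-15 rule might apply. That reading would remove the one-way error but still misclassify about 25%. The stated wording points to the 1st, because only the exceptions separate start from end dates, and SAP 6.1.6 uses concomitant vaccination for COVID-19 doses before as well as during the study.

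Third, sites check eligibility at Visit 1, must record the date and are source-verified, and the event is only weeks old. This limits how many records are affected; it does not make the rule suitable for them.

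A reader might infer three stronger points that the documents do not support:

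- **A mirror-image error of similar size after dosing.** Diary collection covers Days 1 to 30, and a vaccine reported at Visit 2 (30 to 42 days) cannot be later than Visit 2. For a dose on 10 November with Visit 2 on 10 December, every December date reported at that visit is inside the 30 days.
- **A comparable failure for the influenza exception.** Every prior-month dose passes the 14-day limit after imputation, but only about 10% to 11% truly fall inside it, so about nine in ten are classified correctly.
- **A failure of the 90-day immunoglobulin look-back in code 2040.** The text of that code contains no such look-back.

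**Conclusion.** The point holds in conditional form. The SAP states a rule that does not fit a pre-dose washout check and does not say that it is kept out of that check. If it is used there, a prior-month vaccine with a missing day passes on 98% to 99.5% of dosing dates, while on average 47% to 50% of such doses are inside the window. The averages rest on a uniform true day and evenly spread dosing dates, and vary strongly with the dosing day.

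A reader might go on to infer that the lot-consistency conclusion is threatened. The documents do not support that. The number of incomplete dates is unknown, lots are randomised and blinded, and the misclassification should be non-differential, so any shift in the GMC ratios is expected to be small. What is at stake is the accuracy and pre-specification of the PPS.

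**What to change.** In SAP 6.2.2.1, state that the adverse-event imputation is not used to assign codes 1040, 2010 or 2040. Then specify:

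1. Query the exact date first.
2. If it stays unknown, test the earliest and latest possible dates, bounded by the study-dose date, the visit at which the product was reported and any before/after flag.
3. Assign the code if the whole range is inside the protocol window; do not assign it if the whole range is outside.
4. If the range straddles the limit, apply one rule fixed before unblinding, for example eliminate and flag, and report the number of such participants.
5. Use the windows and exceptions already in protocol 5.2.2 and code 1040, including those for influenza vaccines and emergency mass vaccination, and say whether day 30 is inside.

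Keep the present rule for adverse event onset and descriptive tables.

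The cost is a few lines of SAP text, some programming and some date queries. The PPS may lose a few participants, some of them compliant: in the 10 November example, eliminating on a straddling range would also remove the 10 or 11 of 31 October dates that lie outside the window.
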